16.0 Statistical Considerations and Methodology

16.1 Overview:

This is a Phase II study designed to assess the eradication of minimal residual disease (MRD) as well as the toxicity associated with ibrutinib used as maintenance therapy in CLL patients who achieve a PR, nPR, CCR, CRi, or CR post-induction therapy but who have residual disease (i.e. MRD positive).

16.11 Primary Endpoint:

The primary endpoint of this trial is the rate of confirmed MRD-negative response at any time during treatment with ibrutinib maintenance. A confirmed MRD-negative response is defined as an achievement of MRD-negative status in both the blood and the bone marrow on two consecutive evaluations at least three months apart. Confirmed MRD-negative response will be evaluated using all cycles of treatment. Throughout Section 16.0, confirmed MRD-negative response will be considered synonymous with "success" unless specified otherwise. All patients meeting the eligibility criteria who have signed a consent form and have begun treatment will be evaluable for confirmed MRD-negative response, with the exception of patients who are determined to be a major treatment schedule violation.

16.2 Statistical Design:

16.21 Decision Rule:

Prior clinical investigations have evaluated eradication of the MRD with consolidation treatment post induction therapy and these suggest the importance of MRD eradication after first-line therapy. None of these studies have investigated primary maintenance after first-line induction treatment. Two ongoing studies (mentioned in the introduction) have been initiated, but no data is available. Therefore, any indication of benefit with ibrutinib maintenance therapy will be considered promising.

The largest success proportion where the proposed treatment regimen would be considered ineffective in this population is 5%, representing a response by chance alone. The smallest success proportion that would warrant subsequent studies with the proposed regimen in this patient population is 20%. The following one-stage binomial design uses 32 evaluable patients to test the null

hypothesis that the true success proportion in a given patient population is at most 5%.

16.211 **Final Decision Rule:** Enter 32 evaluable patients into the study. If 3 or fewer successes are observed in the first 32 evaluable patients, we will consider this regimen ineffective in this patient population and terminate this study. Otherwise, if the number of successes is at least 4, this will be considered evidence of promising activity and the treatment may be recommended for further testing in subsequent studies.

16.212 **Over Accrual:** If more than the target number of patients are accrued, then the additional patients will not be used to evaluate the stopping rule or used in any decision making process. Analyses involving over accrued patients are discussed in Section 16.34.

16.22 **Sample Size:**

The phase II study design to be used is fully described in section 16.21. A maximum of 32 evaluable patients will be accrued onto this phase II study unless undue toxicity is encountered. We anticipate accruing an additional 3 patients to account for ineligibility, cancellation, major treatment violation, or other reasons. Maximum projected accrual is 35 patients.

16.23 **Accrual Rate and Study Duration:** The anticipated accrual rate is approximately 1-2 patients per month. Therefore, the accrual period for this phase II study is expected to be about 2 years. The final analysis can begin approximately 2.5 years after the trial begins, i.e. as soon as the final patient accrued to this trial has been followed for at least 6 months.

16.24 **Power and Significance Level:** Assuming that the number of responses is binomially distributed, with a significance level of 7%, the probability of declaring that the regimen warrants further studies (i.e., statistical power) can be tabulated as a function of the true success proportion as shown in the table below.

| If the true success proportion is... | 0.05 | 0.10 | 0.15 | 0.20 |
|--|------|------|------|------|
| Then the probability of declaring that the regimen is promising and warrants further study is... | 0.07 | 0.40 | 0.73 | 0.91 |

16.25 **Other Considerations:** Toxicity, quality/duration of response, and patterns of treatment failure observed in this study, as well as scientific discoveries or changes in standard care will be taken into account in any decision to terminate the study.

16.3 **Analysis Plan:**

The analysis for this trial will commence at planned time points (see 16.2) and at the time the patients have become evaluable for the primary endpoint. Such a decision will be made by the Statistician and Study Chair in accordance with CCS Standard Operating Procedures, availability of data for secondary endpoints (e.g., laboratory correlates), and the level of data maturity. It is anticipated that the earliest date in which the results will

be made available via manuscript, abstract, or presentation format is when the last patient has been followed for at least 6 months.

16.31 Primary Endpoint:

- 16.311 Definition: The primary endpoint of this trial is the rate of confirmed MRD-negative response. A confirmed MRD-negative response is defined as an achievement of MRD-negative status in both the blood and the bone marrow on two consecutive evaluations at least 3 months apart. Confirmed MRD-negative response will be evaluated using all cycles of treatment. All patients meeting the eligibility criteria who have signed a consent form and have begun treatment will be evaluable for response, with the exception of patients who are determined to be a major treatment schedule violation.
- 16.312 Estimation: The proportion of successes will be estimated by the number of successes divided by the total number of evaluable patients. Ninety-five percent exact binomial confidence intervals for the true success proportion will be calculated.

16.32 Secondary Endpoint:

- 16.321 Duration of MRD-negative response is defined in patients who have achieved a confirmed MRD-negative response as the time from the earliest date that the patient was noted as having MRD-negative response in both the blood and bone marrow until the first notation of MRD positive disease in the blood or the bone marrow. The distribution of duration of MRD-negative response will be estimated using the method of Kaplan-Meier.⁵⁸
- 16.322 Time to MRD-negative response is defined in patients who have achieved a confirmed MRD-negative response as the time from the date of registration to the earliest date that the patient was noted as having MRD-negative response in both the blood and bone marrow. Time to MRD-negative response will be summarized descriptively (median, range).
- 16.323 Time to requirement of next therapy: A landmark analysis will be conducted to evaluate time to requirement of next therapy for patients who achieve a confirmed MRD-negative response in both the blood and bone marrow vs. those who remain MRD-positive, as assessed at 48 weeks (end of 12 cycles; +/- 4 weeks). Patients who discontinue treatment before 48 weeks are excluded from this analysis. Time to requirement of next therapy will be defined as the time from the 48 week MRD evaluation until the time of initiation of subsequent treatment for progressive CLL. The distribution of time to requirement of next therapy will be estimated using the Kaplan-Meier method and log-rank statistics will be utilized to evaluate differences between the two groups.
- 16.324 Progression-free survival: A landmark analysis will be conducted to evaluate progression-free survival for patients who achieve a confirmed

MRD-negative response in both the blood and bone marrow vs. those who remain MRD-positive, as assessed at 48 weeks (end of 12 cycles; +/- 4 weeks). Patients who discontinue treatment before 48 weeks are excluded from this analysis. Progression-free survival will be defined as the time from the 48 week MRD evaluation until the time of disease progression per the IWCLL criteria or death due to any cause. The distribution of progression-free survival will be estimated using the Kaplan-Meier method and log-rank statistics will be utilized to evaluate differences between the two groups.

16.325 Adverse Events: Platelets and hemoglobin will be graded according to the Grading Scale for Hematologic Adverse Events in CLL Studies in Appendix V. The maximum grade for each type of adverse event, regardless of causality, will be recorded and reported for each patient, and frequency tables will be reviewed to determine adverse event patterns. Adverse events will continue to be recorded and reported up to 30 days after the last day of study drug treatment.

16.33 Correlative Analyses. The reports on the correlative will be descriptive as they are exploratory in nature.

16.332 Study of the impact of ibrutinib treatment on mood is exploratory in nature. Reports of these correlative analyses will be descriptive.

16.34 Over Accrual: If more than the target number of patients are accrued, then the additional patients will not be used to evaluate the stopping rule or used in any decision making processes; however, they will be included in final point estimates and confidence intervals.

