8. Minimal residual disease: MRD assessment will be done at baseline, during the treatment phase and then during the observation phase (no treatment). The MRD will be done on peripheral blood and / or bone marrow aspirate using flow cytometry standardized Mayo Clinic panel. In general bone marrow aspirate evaluation will only be required when the peripheral blood is recorded at least twice (at two separate evaluation 3 months apart) to be negative. If blood is positive for MRD assessment, then bone marrow aspirate evaluation for the MRD will not be needed and can be deferred. **MRD assessment in the Blood:** (a) **Baseline:** all patients will have MRD assessed in the peripheral blood prior to initiating the study. (b) **During treatment phase:** all patients will have MRD assessed in the peripheral blood every 3 cycles. If the ibrutinib maintenance treatment is held > 21 days for toxicity or for any other reason(s) then the MRD testing will be delayed to accommodate 3 treatment cycles prior to testing. (c) **During observation period:** all patients will have MRD assessed within 4 weeks of completion of the last treatment cycles and thereafter every 3 months (if they are MRD negative) and every 6 months (if they are MRD+) for a maximum follow-up of 2 years or until initiation of subsequent treatment for relapsed disease (whichever happens first). **MRD assessment in the Bone marrow aspirate:** The schedule of assessment of the bone marrow aspirate for MRD will be different and dependent upon the results of the MRD status in the blood. (a) **Baseline:** If the peripheral blood MRD results are positive then a BM aspirate assessment for MRD will not be needed. If the peripheral blood MRD results are negative, then a BM aspirate assessment for MRD will be needed. (b) **During the treatment phase:** The MRD assessment of the Bone marrow aspirate will only be required once the peripheral blood MRD is recorded to be negative for at least 2 evaluations that are separated at least 3 months apart. If the blood evaluation demonstrates positivity for MRD, then Bone marrow aspirate evaluation will not be required and can be deferred until the peripheral blood is noted to be negative x 2. (c) **During the observation period:** The MRD assessment of the Bone marrow aspirate will only be required if the post treatment peripheral blood assessment (i.e., that done within 4 weeks of the last treatment dose) was noted to be negative. If the post treatment blood evaluation was noted to be positive, then no bone

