16.35 Data & Safety Monitoring

16.351 The principal investigator(s) and the study statistician will review the study at least every quarter to identify accrual, adverse events, and any endpoint problems that might be developing. The Mayo Clinic Cancer Center (MCCC) Data Safety Monitoring Board (DSMB) is responsible for reviewing accrual and safety data for this trial at least twice a year, based on reports provided by the MCCC Statistical Office.

16.352 Adverse Event Stopping Rule: The stopping rule specified below is based on the knowledge available at study development. We note that the rule may be adjusted in the event of either (1) the study re-opening to accrual or (2) at any time during the conduct of the trial and in consideration of newly acquired information regarding the adverse event profile of the treatments under investigation. The study team may choose to suspend accrual because of unexpected adverse event profiles that have not crossed the specified rule below.

Accrual will be temporarily suspended to this study if at any time we observe events considered at least possibly related to study treatment (e.g., an adverse event with attribute specified as "possible," "probable," or "definite") that satisfy either of the following:

- If 3 or more of the first 12 treated patients experience a grade 4 or higher non-hematologic adverse event at least possibly related to treatment.
- If after the first 12 patients have been treated, 25% of all patients experience a grade 4 or higher non-hematologic adverse event at least possibly related to treatment.

We note that we will review grade 4 and 5 adverse events deemed "unrelated" or "unlikely to be related," to verify their attribution and to monitor the emergence of a previously unrecognized treatment-related adverse event.

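### Eligible, treated patients can leave the primary denominator through an undefined exclusion and are in effect replaced; a minor point that a wording change removes

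*Combined protocol and SAP*

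**What the plan says.** Section 16.11 states that eligible, consented patients who have begun treatment "will be evaluable for confirmed MRD-negative response, with the exception of patients who are determined to be a major treatment schedule violation". Section 16.311 repeats the exception: "with the exception of patients who are determined to be a major treatment schedule violation". The excluded patients have therefore met the entry criteria and taken study drug. Ineligible patients and those who cancel before treatment are handled separately, in 13.3 and 13.4.

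The same set drives both the decision and the estimate. Section 16.211 sets the rule: "If 3 or fewer successes are observed in the first 32 evaluable patients", the regimen is considered ineffective, and at least 4 is promising. Under 16.312 the rate is "estimated by the number of successes divided by the total number of evaluable patients", with an exact 95% interval. Section 16.22 plans "an additional 3 patients to account for ineligibility, cancellation, major treatment violation, or other reasons", for a maximum of 35. It uses a slightly different term from 16.11, also undefined.

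Section 16.34 says of over-accrued patients that "they will be included in final point estimates and confidence intervals". It does not say this of excluded violators. No analysis of the primary endpoint in all eligible treated patients is planned. The accrual-suspension rule in 16.352, by contrast, counts treated patients: "If 3 or more of the first 12 treated patients experience".

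**The concern.** The exclusion applies after treatment has begun, in an open single-arm trial in which MRD is read in blood every 3 cycles. With no definition and no stated separation from MRD results, the success rate depends partly on who is judged a violator.

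The direction of any effect depends on who is removed:

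- If those removed tend to be non-successes, the rate and the chance of a false promising result both rise.
- If one of them is a success, a real response is lost.
- If removal is unrelated to outcome, the rule keeps its properties.

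The first case is plausible but not shown. Success needs negative blood and marrow on two consecutive evaluations at least 3 months apart, so a patient who is off schedule may have fewer chances to document it. The cut-off is 4 successes, so single patients matter when the result is close to it.

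**Working it through.** **Inputs from the plan.** Null rate 5% and target rate 20% (16.21); 32 evaluable patients, promising if at least 4 succeed (16.211); 3 extra patients, maximum 35 (16.22); significance level 7% and power table (16.24).

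**Assumption.** The documents do not give the number of violators, k. I use 0 to 3. Three is the upper case within planned accrual, because those places also cover ineligibility, cancellation and other reasons.

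**1. Reproduce the plan.** P(X ≥ 4) = 1 − Σ C(n,x) pˣ (1−p)ⁿ⁻ˣ for x = 0 to 3. With n = 32 and p = 0.05:

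1 − (0.19371 + 0.32625 + 0.26615 + 0.14008) = 1 − 0.92619 = 0.0738

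At p = 0.10, 0.15 and 0.20 the result is 0.3997, 0.7279 and 0.9069. These match the plan's 0.07, 0.40, 0.73 and 0.91.

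**2. Exclusion unrelated to outcome.** The 32 evaluable patients still succeed at rate p, so the figures in step 1 hold unchanged.

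**3. Exclusion of non-successes only, with replacement.** If k non-successes are removed and accrual continues to 32 evaluable, the success count is that among 32 + k treated patients. The rule becomes at least 4 of 32 + k.

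| k removed | n treated | P(promising), true 5% | P(promising), true 20% |
|---|---|---|---|
| 0 | 32 | 0.0738 | 0.9069 |
| 1 | 33 | 0.0808 | 0.9192 |
| 2 | 34 | 0.0881 | 0.9300 |
| 3 | 35 | 0.0958 | 0.9395 |

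Check for k = 1: the call changes only if the other 32 contain exactly 3 successes and the replacement succeeds. That adds 0.1401 × 0.05 = 0.0070, and 0.0738 + 0.0070 = 0.0808.

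**4. Effect on the estimate at the boundary** (exact 95% intervals).

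- Violators excluded: 4/32 = 12.5% (3.5 to 29.0%)
- One such non-success retained: 4/33 = 12.1% (3.4 to 28.2%)
- Three retained: 4/35 = 11.4% (3.2 to 26.7%)

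**5. Cost of retaining violators.** If the 5% and 20% figures describe all eligible treated patients, the design keeps 0.0738 and 0.9069. If they describe only non-violators, and k of the 32 are certain non-successes, the rule is at least 4 of 32 − k.

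| k retained | False-positive rate, true 5% | Power, true 20% |
|---|---|---|
| 1 | 0.0671 | 0.8930 |
| 2 | 0.0608 | 0.8773 |
| 3 | 0.0548 | 0.8596 |

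**The case against.** The strongest reply is that this hardly matters. Exclusion unrelated to outcome does nothing, one selective removal moves the false-positive rate by 0.7 percentage points, and 0.096 needs all three spare places to go to violators who are all non-successes. A promising result only leads to a possible recommendation for further testing. All of that stands and keeps the point minor.

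Other replies stand in part:

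- **Masking.** Blood MRD results trigger marrow testing, so the treating team must know them. The request can therefore only be that the violation rule is fixed in advance and applied without reference to MRD results.
- **Missing tests.** Patients who stop early for the reasons in 13.1 go directly to event monitoring, where Section 18.0 lists no MRD report. Some violators will have no later MRD test, and the fix needs a rule for them.
- **Other therapy.** Negativity reached after anticancer therapy prohibited by 9.6 should not count as an ibrutinib success.
- **Unseen procedures.** Section 16.3 cites institutional operating procedures, though for analysis timing. Whether they define the term cannot be checked, so the statement is only that these documents do not.

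Three stronger readings are tempting and unsupported. A reader might infer that patients who stop for toxicity, or have a permitted hold, drop out of the denominator. By default 16.11 keeps them in, and after a long hold "for toxicity or for any other reason(s) then the MRD testing will be delayed to accommodate 3 treatment cycles prior to testing" is all that Section 4.0 footnote 8 prescribes. A reader might look to the interruption limits in Section 8 for a definition, but those govern stopping the drug, not evaluability. A reader might also infer that the stated 7% is wrong, but it reproduces.

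**Conclusion.** The point holds as a minor, cheap improvement. It is not an error in the sample size or the decision rule. The documents allow a post-treatment exclusion from the primary analysis under an undefined term, with in-effect replacement and no analysis that returns those patients.

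Within planned accrual, the largest effect is a rise in the false-positive rate of 0.022 (0.0958 − 0.0738) and a boundary estimate about 1.1 percentage points too high (12.5% − 11.4%). Both require three violators, all non-successes. The number of violators and any link to outcome are assumptions. Nothing in the documents shows that selective exclusion is intended or would occur.

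**What to change.** In 16.11 and 16.311:

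1. Make every eligible, consented patient who starts treatment evaluable for the primary endpoint.
2. Count a schedule violator as a success only if confirmed MRD-negativity is documented on study treatment and before any other anticancer therapy. Otherwise count the patient as a non-success, including when no later MRD test exists.
3. Report the rate excluding violators only as a sensitivity analysis. Define the term in advance, name who applies it, and have it applied without reference to MRD results.

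The first 32 such patients decide, and later ones fall under the existing 16.212 and 16.34. Remove major treatment violation from the reasons for extra accrual in 16.22; the spare places still cover ineligibility and cancellation.

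The cost is wording only, with no new data, sample size or cut-off. The reported rate may be slightly lower. Power falls below 0.91 only if the 20% target was meant for non-violators alone, as in step 5 of the working.

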2.2 Secondary

2.21 Median time to achieve MRD⁻ (negative) status (in blood and in bone marrow) after initiation of ibrutinib maintenance treatment.

2.22 Toxicity profile of ibrutinib as maintenance therapy after frontline induction.

2.23 Durability of the MRD⁻ state (determined from the time of first documentation of MRD⁻ until the first documentation of MRD⁺ (or last date shown to be MRD- for a censor)).

2.24 Time to requirement of next therapy for patients who achieve confirmed MRD⁻ vs. those who remain MRD⁺ disease at 48 weeks (end of 12 cycles).

2.25 Progression free survival (as determined by the IWCLL criteria) among patients who achieve confirmed MRD vs. those who remain MRD⁺ disease at 48 weeks (end of 12 cycles).

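### Goal 2.23 does not limit durability of MRD-negativity to confirmed responders but 16.321 does; if confirmation needs a second marrow, early reverters drop out and about 84 days are guaranteed

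*Combined protocol and SAP*

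**What the plan says.** Section 16.321 defines the duration endpoint for confirmed responders only: "Duration of MRD-negative response is defined in patients who have achieved a confirmed MRD-negative response as the time from the earliest date". The clock runs from the "earliest date that the patient was noted as having MRD-negative response in both the blood and bone marrow until the first notation" of positive disease in either specimen. Section 16.311 defines confirmation as "MRD-negative status in both the blood and the bone marrow on two consecutive evaluations at least 3 months apart". The estimator is plain: "The distribution of duration of MRD-negative response will be estimated using the method of Kaplan-Meier". No landmark or delayed entry is mentioned.

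Goal 2.23 describes durability as "determined from the time of first documentation of" MRD-negativity until positivity is first documented. It neither requires confirmation nor names a specimen. The next goal, 2.24, does require confirmation: "Time to requirement of next therapy for patients who achieve confirmed MRD⁻ vs. those who remain MRD⁺ disease at 48 weeks". Goal 2.25 does so too.

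On the schedule, Section 4.0 (footnote 8) and Section 11.3 have blood tested every 3 cycles. On treatment, marrow is required only after two negative bloods at least 3 months apart. Neither place expressly schedules a second marrow.

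**The concern.** Entry to the 16.321 analysis depends on a later result (the second negative), while time is counted from before that result. On the literal reading of 16.311, a patient who is negative in both specimens once, positive at the next evaluation and never confirmed afterwards does not appear in the curve. Those who remain have, in the ordinary case, one interval in which they could not fail. This is guarantee time, and it makes negativity look longer-lasting than it is among everyone who reached it.

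The protocol gives this figure some weight. Section 1.3 names durability of MRD-negativity among the study's distinctive questions, and Section 16.25 lists duration of response among the considerations in a decision to terminate. Sections 16.323 and 16.324 avoid the same problem by counting time from the 48-week evaluation that defines the groups.

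**Working it through.** **The plan's own figures.** None is given for duration. For the primary rule (at least 4 successes in 32), the exact binomial gives 0.0738, 0.3997, 0.7279 and 0.9069 at true rates 0.05, 0.10, 0.15 and 0.20. These match the tabulated 0.07, 0.40, 0.73 and 0.91. Nothing below alters them.

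**Inputs.**
- MRD interval: 3 cycles (Section 4.0, footnote 8) of 28 days (Section 7.1), so g = 84 days; 84 / 30.44 = 2.76 months.
- Visit window of 4 days either way (Section 4.0): the gap between two visits is 76 to 92 days, or 2.50 to 3.02 months.
- True durability: not in the documents. Assumption: exponential, median m of 6 to 36 months.

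**Direction.** Let S(t) be durability from the first dual-negative date among all who reach it. If confirmation requires remaining negative to g, the 16.321 curve equals 1 up to g and S(t)/S(g) afterwards. This is never below S(t), whatever the shape of S. It leaves aside patients who revert and confirm later.

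**Size under the exponential assumption.** S(g) = 2^(-g/m). The share dropped is 1 - S(g). Setting 2^(-(t-g)/m) = 1/2 gives a reported median of m + g. The 12-month estimate is 2^(-12/m) for all first dual-negatives and 2^(-(12-g)/m) for the confirmed group.

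| True median (months) | S(g) | Dropped | Median under 16.321 | Rise | 12-month, all | 12-month, confirmed |
|---|---|---|---|---|---|---|
| 6 | 0.727 | 27.3% | 8.76 | 46% | 0.25 | 0.34 |
| 12 | 0.853 | 14.7% | 14.76 | 23% | 0.50 | 0.59 |
| 24 | 0.923 | 7.7% | 26.76 | 11% | 0.71 | 0.77 |
| 36 | 0.948 | 5.2% | 38.76 | 8% | 0.79 | 0.84 |

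**Visit grid.** Loss of negativity is seen only at visits. Simulating detection at the next 84-day visit gives medians of 8.28, 13.80 and 24.84 months for all first dual-negatives, at true medians of 6, 12 and 24. The confirmed group timed from the first negative gives 11.04, 16.56 and 27.60. The shift is again one interval, 2.76 months.

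**In patients.** At the 20% design rate, 0.20 × 32 = 6.4 confirmed responders are expected. First dual-negatives would number 6.4/S(g), so those dropped number about 2.4, 1.1, 0.5 and 0.35 for true medians of 6, 12, 24 and 36 months.

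**Sensitivity.**
- If 84 days is judged short of 3 months and the next visit is needed, g = 168 days (5.52 months). The shares dropped become 47%, 27%, 15% and 10%.
- With an assumed mix of 30% transient (median 3 months) and 70% durable (median 24 months), 20% are dropped. The median is 12.7 months for all first dual-negatives and 19.4 for the confirmed group timed from the first negative.
- If two negative bloods plus one negative marrow count as confirmation, the first dual-negative date is in effect the confirmation date. Then g is near 0, S(g) is near 1, and the effect disappears.

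**The case against.** Section 16.321 states its population openly, and 16.322 uses the same population and the same date, so time to response and duration join up. Duration among confirmed responders is a legitimate conditional quantity. Patients who never confirm still count as non-successes in the primary rate under 16.312. All of this stands, and it is why the confirmed-responder curve should be kept. It does not make that curve an answer to goal 2.23, whose population is wider.

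A reader might infer that the start date in 16.321 contradicts goal 2.23. It does not: both start at first documentation. Moving the clock to confirmation would itself depart from the goal. The difference is in the population and possibly the specimen. The specimen can work the other way: Section 11.3 words negativity as blood or marrow, and on-treatment marrow follows two negative bloods. A goal 2.23 clock started on blood alone would therefore begin at least one interval earlier than the 16.321 clock for the same patient.

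A reader might also infer that no admitted patient can fail in the first interval. That is too strong. Confirmation may come in any cycle, so a patient who is negative, then positive, then negative twice is a confirmed responder. Read literally, 16.321 gives that patient an event at the first interval.

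Nor is early flatness evidence by itself, since any curve on this schedule is flat until the next visit. What matters is whether a drop can occur at that visit.

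**Conclusion.** The mismatch in population between goal 2.23 and 16.321 is plain on the text. The guaranteed time is conditional: it follows if 16.311 is applied as written, and it is near zero if one marrow is enough. On the literal reading the direction is upward, and the shift in the median is about 2.8 months under exponential durability. That is about 8% of a 36-month median and 46% of a 6-month one. The documents give no durability figure, so the relative size cannot be narrowed further. With 4 to 7 confirmed responders likely to be in the curve (the cut-off, and about the number expected at 20%), the loss of one early reverter would be visible.

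The documents do not support reading this as a flaw in the trial's main result. The endpoint is secondary, has no test or threshold attached, and does not enter the primary decision rule or the sample size. It is a minor but worthwhile correction.

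**What to change.** In 16.321, add a Kaplan-Meier curve of all patients from their first date negative in both blood and marrow, counting a positive at the next evaluation as an event, and name it as the analysis answering goal 2.23. Patients with no later MRD result are censored at their last negative date, as goal 2.23 already provides.

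Keep the confirmed-responder curve and label it as conditional on confirmation. State that, for a patient who reverts before later confirming, its clock starts at the first negative of the confirmed pair.

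The added curve uses results already collected and needs no new visits or patients. The cost is a short addition to 16.321 and a slightly shorter reported duration.
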